5.3.1. Binary Endpoint

For the binary response endpoints (eg, SDAI remission rates), subjects with missing values will be handled by:

- non-responder imputation (NRI) method, ie, setting any missing values to be non-responsive (0)
- will be used as observed (ie, excluding any missing values from analysis)

5.3.2. Continuous Endpoints

For non-patient reported outcome variables, the missing values will be handled as following:

- For continuous endpoints measured longitudinally, the missing values post-baseline will be handled in a linear mixed-effect model with repeated measures for this continuous variable, where the values are assumed to be missing at random.
- For the continuous endpoint not measured longitudinally, the post-baseline missing values will be:
 - as observed (ie, excluding any missing values from analysis);
 - imputed using last observation carried forward (LOCF).

For PRO endpoints, rules suggested by the developers of these PROs will be followed in calculating the values of a given component at a scheduled assessment. If these rules are not enough for imputing a value, then the missing values will be handled in the same way as non-patient reported outcome variables.

6. ANALYSES AND SUMMARIES

6.1. Primary Endpoint(s)

The primary efficacy analysis will be conducted on simple disease activity index (SDAI) change from baseline at Week 8. Analysis will include data on PF-06651600 and placebo arms.

Analyses of the primary endpoint will be based on ITT population.

6.1.1. Primary Analysis

The primary analysis will be based on the Bayesian analysis outlined in Appendix 4.

6.1.2. Sensitivity/Robustness Analyses

There are 3 sets of analyses.

Set 1:

The sensitivity analysis will be based sensitivity prior models on the Bayesian analysis outlined in [Appendix 4](#).

Set 2:

- Missing data imputation
 - Observed
 - LOCF
- ANCOVA (see [Section 5.2.2](#))
 - Baseline SDAI as a covariate
 - Baseline SDAI and previous anti-TNF use as covariates

Set 3:

- Missing data imputation – none (Observed).
- MMRM (see [Section 5.2.2](#)) for analysis of change from baseline in SDAI at Weeks 1, 2, 4, 6, and 8.
 - Baseline SDAI as a covariate
 - Baseline SDAI and previous anti-TNF use as covariates

6.2. Secondary Endpoint(s)

6.2.1. SDAI

Analysis of number of subjects with SDAI remission (SDAI \leq 3.3) and SDAI low disease activity (SDAI \leq 11) at Weeks 4, 6, and 8:

- ITT population set
- Missing data imputation
 - Observed

- NRI
- Normal approximation

Analysis of change from baseline in SDAI at Weeks 1, 2, 4, 6, and 8:

- ITT population set
- Missing data imputation – none (Observed)
- MMRM

6.2.2. DAS

For DAS28-3 (ESR), DAS28-3 (CRP), DAS28 -4 (ESR), and DAS28-4 (CRP), analysis of number of subjects with DAS28 remission (DAS<2.6) and DAS28 low disease activity (DAS28<3.2) at Weeks 4, 6, and 8:

- ITT population set
- Missing data imputation
 - Observed
 - NRI
- Normal approximation

Analysis of change from baseline in DAS28-3 (ESR), DAS28-3 (CRP), DAS28 -4 (ESR), and DAS28-4 (CRP)SDAI at Weeks 1, 2, 4, 6, and 8:

- ITT population set
- Missing data imputation – none (Observed)
- MMRM

6.2.3. hsCRP

Analysis of change from baseline in hsCRP at Weeks 1, 2, 4, 6, and 8:

- ITT population set
- Missing data imputation – none (Observed)
- MMRM

6.2.4. Tender/Painful and Swollen Joint Count

Analysis of change from baseline in the Tender/Painful and Swollen Joint Count (28) at Weeks 1, 2, 4, 6, and 8:

- ITT population set
- Missing data imputation – none (Observed)
- MMRM

6.2.5. PhGA of Arthritis

Analysis of change from baseline in PhGA of arthritis at Weeks 1, 2, 4, 6, and 8:

- ITT population set
- Missing data imputation – none (Observed)
- MMRM

6.3. PRO Endpoints

Analysis of change from baseline in for outcomes research endpoints at Weeks 1, 2, 4, 6, and 8:

- Endpoints are PAAP VAS, PtGA VAS, and HAQ-DI
- ITT population set
- Missing data imputation – none (Observed)
- MMRM

6.4. CCI

[REDACTED], only ACR20, ACR50, and ACR70 rate will be summarized:

- CCI [REDACTED]
- [REDACTED]
- [REDACTED]
- [REDACTED]
- [REDACTED]

Additional statistical analyses of other exploratory endpoints (including PK analysis) will be provided in a separate document.

6.5. Subset Analyses

Summary statistics for the SDAI endpoints will be presented by baseline smoking status and by previous anti-TNF use.

6.6. Baseline and Other Summaries and Analyses

6.6.1. Baseline Summaries

Demographics and medical history variables as defined in [Section 3.5](#) will be summarized by treatment group.

6.6.2. Study Conduct and Subject Disposition

Subject evaluation groups will show end of study subject disposition and will show which subjects were analyzed in the ITT analysis set, and as well as for safety. Frequency counts will be supplied for subject discontinuations by treatment.

Data will be reported in accordance with Pfizer reporting standards.

6.6.3. Study Treatment Exposure

A summary of compliance and the number of doses received as well as the median total dose by visit and treatment group will be provided.

6.6.4. Concomitant Medications and Non-Drug Treatments

All concomitant medication(s) as well as non-drug treatment(s) will be provided in the listings.

6.7. Safety Summaries and Analyses

Safety analysis will be based on the SAF analysis set.

All clinical AEs, SAEs, treatment-emergent signs and symptoms (TEAEs), withdrawal due to AEs, ECGs, vital signs and safety laboratory data will be reviewed and summarized on an ongoing basis during the study to evaluate the safety of subjects.

Safety data will be presented in tabular and/or graphical format and summarized descriptively, where appropriate. All safety endpoints will be listed and summarized in accordance with Pfizer Data Standards. Categorical outcomes (eg, AEs) will be summarized by subject counts and percentage. Continuous outcome (eg, blood pressure, pulse rate, etc) will be summarized using N, mean, median, standard deviation, etc. Change from baseline in laboratory data, ECGs and vital signs will also be summarized. Subject listings will be produced for these safety endpoints accordingly.

6.7.1. Adverse Events

It should be recognized that most studies are not designed to reliably demonstrate a causal relationship between the use of a pharmaceutical product and an adverse event or a group of adverse events. Except for select events in unique situations, studies do not employ formal adjudication procedures for the purpose of event classification. As such, safety analysis is generally considered as an exploratory analysis and its purpose is to generate hypotheses for further investigation. The 3-tier approach facilitates this exploratory analysis.

The analyses of adverse events under the 3-tier approach are considered exploratory. There will be no adjustment for multiple comparisons or stratification factors in the analyses unless specified.

Nominal p-values (Tier-1 events only) and 95% confidence intervals (Tier-1 and Tier-2 events) will be provided for between treatment differences in the percentage of patients with events. Reporting p-values and confidence intervals will follow Pfizer standards.

6.7.2. Laboratory Data

Laboratory data will be listed and summarized by treatment and visit in accordance with the Pfizer reporting standards.

6.7.3. Vital Signs

Absolute values and changes from baseline in systolic and diastolic blood pressure, respiratory rate, pulse rate and temperature will be listed summarized by treatment and visit in accordance with the Pfizer reporting standards.

6.7.4. Electrocardiogram

Categorical summary tables will be summarized by treatment and visit using Pfizer reporting standards. A listing of ECG comments on findings and normal/abnormal results will be provided.

6.7.5. Physical Examination

All physical exam data will be provided in the listings.

7. INTERIM ANALYSES

No interim analysis is planned. Final analyses will follow the official database release.

8. REFERENCES

None.

9. APPENDICES

Appendix 1. SUMMARY OF EFFICACY ANALYSES

All efficacy analyses will be based on ITT set. Treatment groups will be PF-06651600 and placebo.

Primary Efficacy Endpoint	Statistical Method	Missing Data
Change from baseline in SDAI at Week 8	ANCOVA with baseline SDAI as a covariate	Observed
Change from baseline in SDAI at Week 8	ANCOVA with baseline SDAI as a covariate	LOCF
Change from baseline in SDAI at Week 8	ANCOVA with baseline SDAI and anti-TNF use as covariates	Observed
Change from baseline in SDAI at Week 8	ANCOVA with baseline SDAI and anti-TNF use as covariates	LOCF
Change from baseline in SDAI at Week 8	Bayesian analysis of posterior distributions of the SDAI scores and placebo adjusted change from baseline	-

Secondary Efficacy Endpoints	Statistical Method	Missing Data
SDAI remission and low disease activity at Weeks 4, 6, and 8	Normal approximation	Observed
SDAI remission and low disease activity at Weeks 4, 6, and 8	Normal approximation	NRI
DAS28-3 (ESR), DAS28-3 (CRP), DAS28 -4 (ESR), and DAS28-4 (CRP) remission and disease activity at Weeks 4, 6, and 8	Normal approximation	Observed
DAS28-3 (ESR), DAS28-3 (CRP), DAS28 -4 (ESR), and DAS28-4 (CRP) remission and disease activity at Weeks 4, 6, and 8	Normal approximation	NRI

Change from baseline in SDAI at Weeks 1, 2, 4, 6, and 8	MMRM	Observed
Change from baseline in DAS28 (eg, DAS28-3 (ESR), DAS28-3 (CRP), DAS28 -4 (ESR), and DAS28-4 (CRP)) at Weeks 1, 2, 4, 6, and 8	MMRM	Observed
Change from baseline in hsCRP at Weeks 1, 2, 4, 6, and 8	MMRM	Observed
Change from baseline in in the Tender/Painful and Swollen Joint Count (28) at Weeks 1, 2, 4, 6, and 8	MMRM	Observed
Change from baseline in PhGA of Arthritis at Weeks 1, 2, 4, 6, and 8	MMRM	Observed

Outcomes Research Endpoints	Statistical Method	Missing Data
-----------------------------	--------------------	--------------

Change from baseline in in PAAP VAS and PtGA of Arthritis VAS at Weeks 1, 2, 4, 6, and 8	MMRM	Observed
Change from baseline in in the HAQ-DI at Weeks 1, 2, 4, 6, and 8	MMRM	Observed

CCI

CCI

ACR20, ACR50, and ACR70 at Weeks 4, 6, and 8	CCI	
ACR20, ACR50, and ACR70 at Weeks 4, 6, and 8	CCI	

Appendix 2. DETAILS OF VISIT WINDOWS

Visit windows will be used for efficacy variables, and for any safety data that display/summarize by study visit. For other endpoints (eg, ECG, vital signs), visit windows will be applied for summary statistics by study visits if required.

Visit Label	Target Day	Definition [Day window]
Screening		Days -35 to Day 0
Baseline	Day 1, Randomization	Day 1
Week 1	8	Days 2 to 11
Week 2	15	Days 12 to 22
Week 4	29	Days 23 to 36
Week 6	43	Days 37 to 50
Week 8	57	Days 51 to 64
Follow Up/End of Study		
Week 10	71	Days 65 to 78
Week 12	85	Days 79 to -

For the lab values, if the calculated study day for the labelled baseline visit is not study Day 1, but falls within 40 days before the start of the study dosing, then that data should be used for the baseline instead of leaving baseline missing.

For the other values, if the calculated study day for the labelled baseline visit is not study Day 1, but falls before the start of the study dosing, then that data should be used for the baseline instead of leaving baseline missing.

If two or more visits fall into the same window, keep the one closest to the Target Day. If two visits are equaled distant from the Target Day in absolute value, the later visit should be used.

Safety analysis may follow Pfizer standard.

Appendix 3. DATA DERIVATION DETAILS

A patient is said to have achieved the ACR20 criteria⁺ when all of the following bulleted points are true:

- A 20% improvement from baseline in the tender/painful joint count (TCJ28).
- A 20% improvement from baseline in the swollen joint count (SJC28).
- A 20% improvement from baseline in *at least 3* of the following 5 variables:
 1. PhGA of Arthritis;
 2. PAAP VAS;
 3. PtGA of Arthritis VAS;
 4. HAQ disability index;
 5. Results of ESR or CRP blood test (both of which test for inflammation).

ACR50 and ACR70 are defined analogously.

There are many forms of the DAS. The DAS used in this study is the DAS using the 28-count subsets of tender/painful joints and swollen joints, together with either CRP or ESR, to derive the DAS28-3 (CRP), DAS28-4 (CRP), or DAS28-3 (ESR) and DAS28-4 (ESR), which are calculated using the following formulae, respectively:

$$\text{DAS28-4(ESR)} = (0.56 * \text{sqrt(TJC28)} + 0.28 * \text{sqrt(SJC28)} + 0.70 * \text{ln(ESR)} + 0.014 * \text{GH}$$

$$\text{DAS28-3(ESR)} = [0.56 * \text{sqrt(TJC28)} + 0.28 * \text{sqrt(SJC28)} + 0.70 * \text{ln(ESR)}] * 1.08 + 0.16$$

$$\text{DAS28-4(CRP)} = 0.56 * \text{sqrt(TJC28)} + 0.28 * \text{sqrt(SJC28)} + 0.36 * \text{ln(CRP+1)} + 0.014 * \text{GH} + 0.96$$

$$\text{DAS28-3(CRP)} = [0.56 * \text{sqrt(TJC28)} + 0.28 * \text{sqrt(SJC28)} + 0.36 * \text{ln(CRP+1)}] * 1.10 + 1.15$$

where TJC28 is number of painful joints out of 28 joints, SJC28 is number of swollen joints out of 28 joints, GH is the general health or patients' global assessment of disease activity on a 100 mm VAS, ln is the natural logarithm, ESR is in mm/first hour, and CRP is in mg/L.

Handling Missing Joint Counts:

- A missing painful/tender assessment or one NOT DONE at *baseline* is set to “not painful/tender”;
- A missing swollen assessment or one NOT DONE at *baseline* is set to “not swollen”;

- A missing painful/tender assessment or one NOT DONE *post baseline* is set to “painful/tender”;
- A missing swollen assessment or one NOT DONE at *post baseline* is set to “swollen”.

Note that joints marked NOT APPLICABLE are not to be counted in the summation of swollen and painful/tender joints at baseline and post baseline.

Any *new* NOT APPLICABLE for a joint POST BASELINE is set to “painful/tender” and “swollen”.

Any intra-articular injection (baseline and post baseline) sets the joint status to “painful/tender” and “swollen” - on or after the date of the injection.

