4.1. Inclusion Criteria

Subjects must meet all of the following inclusion criteria to be eligible for enrollment into the study.

1. Evidence of a personally signed and dated informed consent document indicating that the subject [or a legally acceptable representative] has been informed of all pertinent aspects of the study.
2. Willing and able to comply with scheduled visits, treatment plan, laboratory tests and other study procedures.
3. Male and female subjects (including Women of Childbearing Potential (WOCBP)) between the ages of 18 and 75 years, inclusive. For subjects >70 years old, the site must discuss subject eligibility with the study team to ensure that these subjects are sufficiently healthy to participate.
4. Female subjects of childbearing potential must test negative for pregnancy at screening visit and baseline visit.
5. Female subjects of nonchildbearing potential must meet at least 1 of the following criteria:
 - a. Achieved postmenopausal status, defined as follows: cessation of regular menses for at least 12 consecutive months with no alternative pathological or physiological cause and have a serum follicle-stimulating hormone (FSH) level confirming the postmenopausal state;
 - b. Have undergone a documented hysterectomy and/or bilateral oophorectomy;
 - c. Have medically confirmed ovarian failure.

All other female subjects (including female subjects with tubal ligations) are considered to be of childbearing potential.

6. Diagnosis of rheumatoid arthritis (RA) and meeting the 2010 American College of Rheumatology (ACR)/European League Against Rheumatism (EULAR) classification criteria (see [Appendix 2](#)) for RA with a Total Score $\geq 6/10$. The duration of time since diagnosis of RA should minimally be sufficient to meet the definition of methotrexate inadequate response (see criteria 10 below).
7. Meets Class I, II or III of the ACR 1991 Revised Criteria for the classification of Global Functional Status in RA (see [Appendix 2](#)).
8. The subject has active disease at both Screening and Baseline, as defined by both:
 - ≥ 6 joints tender or painful on motion; AND
 - ≥ 6 joints swollen;

and

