7.1. Efficacy Assessments

7.1.1. American College of Rheumatology (ACR) Assessments

The specific components of the ACR Assessments (ACR Core Dataset) that will be used in this study are:

1. Tender/Painful Joint count (TJC) (68).
2. Swollen Joint Count (SJC) (66).
3. Patient's Assessment of Arthritis Pain.

4. Patient's Global Assessment of Arthritis.
5. Physician's Global Assessment of Arthritis.
6. C-Reactive Protein (CRP), measured by high sensitivity methodology (hsCRP).
7. Erythrocyte Sedimentation Rate (ESR)
8. Health Assessment Questionnaire – Disability Index (HAQ-DI).

Components of the ACR Core Dataset will be collected at the visits indicated in the [Schedule of Activities](#).

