7.1.3.1. Tender and Swollen Joint Counts (28)

The twenty-eight tender/painful joint count includes the following joints: shoulders, elbows, wrists, metacarpophalangeal joints (MCP), proximal interphalangeal joints (PIP), and knees. Artificial joints will not be assessed. This count will be calculated by Pfizer from the 68 tender/painful joint count assessed by the joint assessor as described in [Section 7.1.2](#).

The twenty-eight swollen joint count measurement will include the same joints as described above for 28 tender/painful joint count, and will be calculated by Pfizer from the 66 swollen joint count assessed for swelling by the joint assessor as described in [Section 7.1.3](#). Artificial joints will not be assessed. Physician assessment should be performed without the knowledge of patient reported outcome measures.

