7.1.5.1. Simple Disease Activity Index (SDAI) Assessment

The SDAI is a continuous composite measure derived components of the ACR Core Dataset. The SDAI will be calculated using the following formula:

$$\text{SDAI} = \text{TJC (using 28 joints)} + \text{SJC (using 28 joints)} + \text{PtGA (0–10 cm scale)} + \text{PhGA (0–10 cm scale)} + \text{and hsCRP (mg/dL)}.^1$$

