7.1.5.2. ACR Responder Analysis

The American College of Rheumatology’s definition for calculating improvement in RA (ACR20) is calculated as a 20% improvement in tender and swollen joint counts and 20% improvement in 3 of the 5 remaining ACR-core set measures: patient’s and physician’s global assessments, pain, disability, and an acute-phase reactant. Similarly, ACR50 and ACR70 are calculated with the respective percent improvement. Components of the ACR Responder Index will be collected as indicated in the [Schedule of Activities](#).

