7.1.6. Disease Activity Score (DAS) Assessments

The Disease Activity Score (DAS) assessment is a continuous composite measure derived using differential weighting given to each component. DAS28 is a measure based on 28 tender and swollen joint counts. DAS28 may be calculated with 3 components (not including assessment of an acute phase reactant) (DAS28-3) or 4 components (DAS28-4 = DAS28-3 + either ESR or CRP). The formulae for calculation of DAS28-4 (CRP) and DAS28-4 (ESR) are presented in [Appendix 6](#). Components of DAS28-3 (CRP),

DAS28-3 (ESR), DAS28-4 (CRP), and DAS28-4 (ESR) will be collected as indicated in the [Schedule of Activities](#).

The components of the DAS 28 arthritis assessment include:

- Tender/Painful Joint Count (28).
- Swollen Joint Count (28).
- CRP or ESR.
- Patient’s Global Assessment of Arthritis.

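### SAP Appendix 3 scores ACR20/50/70 on 28-joint counts, while the protocol's ACR core set uses 68 tender and 66 swollen joints; no visible text declares or explains the change

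*SAP*

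**What the plan says.** **SAP.** Appendix 3 (Data Derivation Details) makes ACR20 depend on "A 20% improvement from baseline in the tender/painful joint count (TCJ28"), on the same improvement in SJC28, and on at least three of five other measures. ACR50 and ACR70 follow the same pattern. The label TCJ28 is evidently a misprint for TJC28. The same appendix defines TJC28 and SJC28 as counts out of 28 joints, so the intended number is not in doubt.

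**Protocol.** Section 7.1.1 introduces its list with "The specific components of the ACR Assessments (ACR Core Dataset) that will be used in this study are". Item 1 is "Tender/Painful Joint count (TJC) (68") and item 2 is the 66-joint swollen count. Section 7.1.5.2 defines ACR20 as 20% improvement in the tender and swollen counts plus "improvement in 3 of the 5 remaining ACR-core set measures".

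Where the protocol wants 28 joints, it says so:
- SDAI (Section 7.1.5.1): "TJC (using 28 joints").
- DAS28 (Section 7.1.6): "DAS28 is a measure based on 28 tender and swollen joint counts".
- The separate 28-joint tender count (Section 7.1.3.1), which "will be calculated by Pfizer from the 68 tender/painful joint count"; the swollen count is derived in the same way from the 66.

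**The concern.** The word "remaining" in the protocol's ACR20 definition makes the two joint counts members of the core set, and Section 7.1.1 gives that core set as 68 and 66 joints. The SAP would therefore report ACR rates for a different measure from the one the protocol describes, under the same name. A subject could be a responder on one set of joints and a non-responder on the other. A reader of the results would have no means of knowing that the 28-joint version had been used, or why.

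The 28-joint version also brings in a gap of its own. Inclusion criterion 8 asks for at least 6 "joints tender or painful on motion" and at least 6 swollen joints, without limiting them to the 28. A subject can therefore enter with a 28-joint count of 0, for which percent improvement is undefined. The visible SAP text has no rule for that case.

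**Working it through.** The plan states no figure on this point, so there is none to reproduce.

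**1. Joints left out** (Protocol 7.1.2, 7.1.3 and 7.1.3.1)
- The 28: shoulders 2 + elbows 2 + wrists 2 + MCP 10 + PIP 10 (thumb IP counted with the PIPs) + knees 2 = 28.
- Outside the 28, tender: temporomandibular 2 + sternoclavicular 2 + acromioclavicular 2 + DIP 8 + hips 2 + ankles 2 + tarsus 2 + MTP 10 + great-toe IP 2 + toe PIP 8 = 40, and 28 + 40 = 68.
- Outside the 28, swollen: 40 − 2 hips = 38, and 28 + 38 = 66.

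**2. Either direction is possible** (constructed counts, not trial data). Improvement = (baseline − follow-up) / baseline.

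| Case | 28 joints | 68 joints | Tender item at 20% |
|---|---|---|---|
| A | 10 to 8: 2/10 = 20% | 20 to 18: 2/20 = 10% | met on 28 only |
| B | 10 to 9: 1/10 = 10% | 20 to 16: 4/20 = 20% | met on 68 only |

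**3. Baseline count of 0**
- 6 active joints placed at random: C(40,6)/C(68,6) = 3.5% for the tender count and C(38,6)/C(66,6) = 3.0% for the swollen count.
- 10 active joints placed at random: C(40,10)/C(68,10) = 0.3% and C(38,10)/C(66,10) = 0.2%.
- 6 active joints, each with a 70% chance of lying in the 28: 0.3^6 = 0.07%.

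So it is possible but uncommon.

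**4. How often the joint items might disagree.** The documents give no joint-level data, so every input here is an assumption:
- baseline tender/swollen counts of 12/8, 20/14 or 28/18;
- 50, 60 or 70% of active joints within the 28;
- mean resolution of 30% or 50%, with each subject's probability drawn from a Beta distribution with a + b = 4, equal inside and outside the 28;
- joints resolve independently given that probability, and no new joints become active;
- the tender and swollen items must both be met.

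This gives 18 scenarios, with 400,000 simulated subjects in each. Share of subjects whose joint items disagree at the 20% level:
- every subject has exactly the stated share of active joints in the 28: 4.7 to 14.0%;
- that share varies binomially between subjects: 5.3 to 15.2%.

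Of about 60 subjects, 4.7% is 2.8 and 15.2% is 9.1, so about 3 to 9 people. The net shift of the joint-item rate (28 minus 68/66) at the 20% level runs from −7.2 to +1.0 percentage points with the fixed share, but is negative throughout, about −7 to −1, with the binomial share. Its sign depends on a modelling choice, so I draw no conclusion about direction.

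**The case against.** **The conflict is inferred.** Section 7.1.5.2 does not itself state a number of joints. Section 7.1.1 is partly a list of what is collected: it has eight items, including both CRP and ESR, so it is not exactly the responder set. SDAI is derived from the same dataset and still uses 28 joints. This stands as far as it goes, and the link does run through the core set. But SDAI names its 28 joints and ACR20 does not, which leaves 68/66 as the natural reading.

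**The SAP may do this.** Protocol Section 9 and SAP Section 2 let the SAP modify the protocol, and an amendment is promised only for major changes to the primary endpoint or its analysis. This stands. A reader might infer that the SAP breaches the protocol; the documents do not support that. The fault is a departure that is not identified or explained. Nor is the SAP version history strong evidence, because it records changes between SAP versions rather than departures from the protocol.

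**Redaction.** The ACR text in SAP Section 3, Section 6.4 and Appendix 1 is partly blacked out, so a reason or a handling rule may stand there. This also stands, and it is why the point is limited to the visible text.

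**Low stakes.** ACR rates are not among the visible primary or secondary endpoints, and the decision rule in SAP Section 5.1 concerns SDAI only. This is correct and limits the weight of the point.

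**Conclusion.** The point holds as an undeclared and unexplained difference in the definition of ACR20/50/70. It reaches only the ACR summaries. The SDAI primary analysis, DAS28 and the listed 28-joint count endpoint rightly use 28 joints and are untouched.

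That responder status can change in either direction follows from the arithmetic alone. The size does not: the range of roughly 5 to 15% at the 20% level is illustrative and rests wholly on the assumptions listed.

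Two stronger readings should be resisted.
- A reader might take the range as an upper limit for disagreement on ACR itself. Within one scenario the three-of-five requirement is common to both versions and can only remove disagreements. But the range moves with the assumed split of joints, would move again if joints inside and outside the 28 responded differently, and does not bound the net shift in the rate.
- A reader might also infer from the missing-joint rules in the same appendix that a wholly missed examination would score every joint as active. Those rules describe states of single joints, and SAP Sections 5.3.2 and 6.1.2 already cover missing values, so I raise no point there.

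**What to change.** In SAP Appendix 3, define ACR20/50/70 as at least 20/50/70% improvement in the 68-joint tender count and in the 66-joint swollen count, plus the same improvement in at least three of the five other measures. Keep 28 joints for SDAI, DAS28 and the 28-joint count endpoint. Correct the label TCJ28 wherever it remains.

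If 28 joints are intended for ACR, say in the SAP that this is a change from the protocol, give the reason, and state how a baseline count of 0 is handled.

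The cost is SAP wording and derivation code. The 68 and 66 joint counts are already in the Schedule of Activities, and the 28-joint counts are computed from them. No new data are needed, and the primary analysis does not change.
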